5.2.6.2.3 Pregnancy

In rare cases, pregnancy might occur in a clinical trial. Once a patient has been enrolled in the clinical trial and has taken trial medication, the investigator must report any drug exposure during pregnancy in a trial participant immediately (within 24 hours) by means of Part A of the Pregnancy Monitoring Form to the sponsor's unique entry point.

Similarly, potential drug exposure during pregnancy must be reported if a partner of a male trial participant becomes pregnant. This requires written consent of the pregnant partner.

Reporting and consenting must be in line with local regulations. The ISF will contain the trial specific information and consent for the pregnant partner.

The outcome of the pregnancy associated with the drug exposure during pregnancy must be followed up and reported to the sponsor's unique entry point on the Pregnancy Monitoring

[figure not shown]
Form for Clinical Studies (Part B). The ISF will contain the Pregnancy Monitoring Form for Clinical Studies (Part A and B).

[figure not shown]
As pregnancy itself is not to be reported as an AE, in the absence of an accompanying SAE and / or AESI, only the Pregnancy Monitoring Form for Clinical Studies and not the SAE form is to be completed. If there is an SAE and / or AESI associated with the pregnancy an SAE form must be completed in addition.

5.2.6.2.4 Safety monitoring and adverse events with additional information collection

Additional details (on top of standard AE and SAE reporting) will be collected in the eCRF for the adverse events:

[figure not shown]
- Acute Kidney Injury (see [section 3.3.3](#) for definition of AKI),
- Adrenal insufficiency,
- Hyperkalaemia,
- Hypotensive event,
- Hypoglycaemic event,
- Events leading to lower limb amputation (LLA),
- Ketoacidosis/ metabolic acidosis,
- Bone fractures.

5.4 ASSESSMENT OF BIOMARKER(S)

This section refers to exploratory biomarkers. Established biomarkers of efficacy and safety are described and discussed in [sections 5.1](#) and [5.2](#).

5.4.1.1 Method and timing of sample collection

Urine – exploratory biomarkers

Urine samples for exploratory biomarkers will be taken from the urine sample collected for safety at the timepoints shown in the [Flow Chart](#).

Plasma aldosterone and cortisol and their precursors

Blood will be drawn into a K-EDTA blood collection tube at multiple time points as indicated in the [PK and aldosterone profile Flow Chart](#).

Plasma

Blood will be drawn into a K-EDTA blood collection tube at the time points indicated in the [Flow Chart](#).

Serum

Blood will be drawn into a serum separation tube at the time points indicated in the [Flow Chart](#).

All urine, plasma and serum samples remaining at the end of the study will be destroyed no later than the sign-off of the separate biomarker report no more than two years after the last patient has completed the trial.

Detailed instructions for biomarker sampling, including handling and shipment of samples will be provided in the laboratory manual in the ISF.

5.4.2 Pharmacogenomic biomarkers

Pharmacogenomics investigates genetic variations to explain and to predict an individual's response to drugs. Therefore, a blood sample for pharmacogenomic testing will be taken from each participant. In case of unexplainable variability in aldosterone level or of PK or PD parameters, DNA may be extracted from these samples and used for exploratory analysis of variants of the aldosterone synthase gene and genes involved in Absorption, Distribution, Metabolism and Excretion (ADME) of drugs. It is not intended to include these data in the final report. However, the data may be part of the report if necessary. All remaining samples will be discarded no later than 2 years after the last patient has completed the trial.

Detailed instructions for pharmacogenomics sampling, including handling and shipment of samples will be provided in the laboratory manual in the ISF.

5.4.2.1 Method of sample collection

One blood sample will be taken from an arm vein in a PAXgene blood DNA drawing tube at the time point indicated in the [Flow Chart](#).

5.4.2.2 Analytical determinations

Genomic DNA will be extracted from blood samples according to standard molecular genetics methods and analysed by Drug Metabolism Enzymes and Transporters (DMET™) analysis or other standard genotyping technologies.

5.5 BIOBANKING

Participation in biobanking is voluntary and not a prerequisite for participation in the trial. Biobanking will only occur after a separate biobanking informed consent has been given in accordance with local ethical and regulatory requirements.

In some countries, for example China, biobanking samples will not be collected due to regulatory reasons.

5.5.1 Methods and timing of sample collection

Sampling will be performed at the time points specified in the [Flow Chart](#).

Plasma banking: Blood will be drawn into a K-EDTA blood collection tube.

Serum banking: Blood will be drawn into a serum separation tube.

Urine banking: Urine will be taken after tubes for exploratory biomarkers (see [section 5.4.1](#)) have been filled. The urine will be taken from the urine sample collected for safety.

As no genetic testing is planned, no dedicated sample will be taken for the analysis of DNA and no DNA will be extracted from any of the biobanking sampled described above.

For all biospecimens collected, detailed instructions on sampling, preparation, processing, shipment and storage are provided in the laboratory manual. Samples will be stored at an external biobanking facility contracted by the sponsor.

[figure not shown]
5.6 OTHER ASSESSMENTS

N/A

5.7 APPROPRIATENESS OF MEASUREMENTS

All measurements performed during this trial are standard measurements and will be performed in order to monitor safety aspects and to determine efficacy, PK and PD markers of empagliflozin and BI 690517 in an appropriate way.

The scheduled measurements are appropriate to assess drug induced changes in kidney function with regards to albuminuria (UACR), and safetywise in vital signs, standard laboratory values, and ECG. While UACR is widely accepted as a PD marker for efficacy in kidney trials, safety lab, vital signs and ECG are standard to examine the safety of the investigational product and to descriptively identify differences between different doses and placebo.

Therefore, the appropriateness of all measurements applied in this trial is given.

6. INVESTIGATIONAL PLAN

6.1 VISIT SCHEDULE

All visits should be scheduled according to the [Flow Chart](#). Each visit date in the Randomised Run-in Period (with its window) is to be counted from Day -56 (first randomisation). All visits in the Treatment Period and Follow-up Period are to be counted from Day 1 (second randomisation). If any visit has to be rescheduled, subsequent visits should follow the original visit schedule. The trial medication packs contain sufficient medication to allow for time windows.

All trial visits should be initiated preferentially in the morning. Patients should be instructed to not take their dose of the study medication at home in the morning of scheduled visit days as they will be dosed whilst at the study site.

Patients do not need to come fasted to study visits, but their fasting status will have to be recorded in the CRF for [REDACTED]. From the first [REDACTED] the patient should only drink water and eat no food unless it is medically needed.

Unscheduled visits will be possible at the discretion of the investigator at any time in order to check the safety of the patient or to provide trial medication e.g. following an interruption. If the reason for removal of a patient from treatment is an adverse event or a clinically significant laboratory test result, the patient must be followed-up until complete resolution or stabilisation of the event or until follow-up is agreed adequate by the Investigator and sponsor.

In the event of force majeure or other disruptive circumstances (e.g. pandemic, war) the investigational plan as per this clinical trial protocol may not be feasible at a site. With the consent of the patient, sponsor and investigator may agree on alternative, back-up or rescue methodology which may include but will not be limited to virtual (remote) patient visits and assessments, home healthcare nurse visits, and direct-to-patient shipments of trial treatment. Such alternative measures will be mentioned in the patient information leaflet. The implementation of these measures will depend on patient's consent, operational feasibility,

local law and regulations. If alternative methodology is implemented, the deviations from the original plan will be precisely documented.

6.2 DETAILS OF TRIAL PROCEDURES AT SELECTED VISITS

Study measurements and assessments should be performed according to the [Flow Chart](#). All assessments should be performed before study drug administration, with the exception of the post-dose PK and aldosterone profile samples.

Where the following assessments occur at a visit they should be performed in the following order:

Vital signs

ECG

Blood draws including trough PK and plasma aldosterone – other PK and plasma aldosterone samples are drawn after drug administration (see [PK and aldosterone Flow Chart](#)). Post dose-serum cortisol at Visit 5 is also drawn after drug administration.

There will be home sampling without a visit at Week -4 ('Visit' 3.1 during Randomised Run-in), Weeks 12 and 13 ('Visits' 9.1 and 9.2 respectively, during the Treatment Period), and at Weeks 16 and 17 ('Visits' FUp1.1 and FUp1.2 respectively, during the Follow-up Period). The patient will be required to collect urine samples for UACR over two consecutive days according to the [FMV and 24-hour Urine Sampling Flow Chart](#) at these times.

In this study the following visits may be performed as Telemedicine Contacts and Home Visits if all local approvals are in place. These contacts are used to help support patients with protocol procedures and compliance (see [section 6.2.1](#) and [6.2.2](#)):

- Telemedicine Contact: Visit 3
- Home Visits: Visits 4, 6, 9, FUp2

All other visits must be performed at the Investigational Site. The only exception to this is in the event of force majeure or other disrupting circumstances where physical patient visits to the sites may not be feasible or may need to be restricted to ensure patient safety. Based on a thorough assessment of the benefits and risks, the following visits may be performed at the patient's home or remotely, e.g. via telephone and/or internet-based means of communication:

- Visit 2 (first randomisation) – may be performed as a home visit only
- Visit 5 (second randomisation) – may be performed as a home visit only
- Visits 7 and 8 (Treatment Period) – may be performed as a home and/or remote visit
- EoT – may be performed as a home and/or remote visit
- FUp1 – may be performed as a home and/or remote visit

Where Visit 2 and/or Visit 5 are conducted as a home visit, eligibility assessment and randomisation must be performed prior to the visit to allow time for the study medication to be shipped to the patient's home.

All deviations from the original schedule of visits and procedures will be documented and the implications considered for the analysis of the trial data.

If blood sampling for central lab at the trial site is not possible, safety lab analyses can be performed at a local lab. The results of the lab tests must be transferred to the investigator who ensures medical review and proper documentation in the eCRF. Minimum required safety lab parameters are listed in [table 5.2.3:2](#). Urine pregnancy tests (for women of childbearing potential only, where required according to the [Flow Chart](#)) may be done at local lab / local doctor, or at home.

In the event of elevated potassium > 5 mmol/L, if the patient is unable or unwilling to return to the investigational site, the BI 690517 or matching placebo should be temporarily interrupted until the patient can return to the investigational site.

If remote visits and/or lab assessments cannot be performed within the time window for the visit, or if patient safety cannot be guaranteed, all randomised study medication needs to be interrupted until the visit and lab assessments can be conducted.

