An individual patient will permanently discontinue BI 690517 / placebo if:

1. The patient's serum potassium measures ≥ 6.0 mmol/L by central or any local laboratory, or ≥ 5.6 mmol/L if down-titration is considered inappropriate.

¹ Where the eGFR drop occurs before the start of BI 690517 / placebo in the Treatment Period (i.e., at Visit 5), but the result is not available until after the patient starts BI 690517/placebo treatment, the patient must still permanently discontinue all randomised study treatment, including BI 690517 / placebo.

2. The patient develops Cushing's syndrome, adrenal insufficiency (including cortisol level $<18 \mu\text{g/dL}$ 30 min (± 5 min) after ACTH application) or the patient's cortisol level is $< 3 \mu\text{g/dL}$ (82.8 nmol/L) at any point in the trial. The patient must be followed according to local guidelines until resolution of the event and the event is going to be reported to the sponsor (see [section 5.2.6.1.4](#)).

An individual patient will permanently discontinue empagliflozin / placebo if:

1. Ketoacidosis is suspected.
2. Fournier's gangrene is suspected.

If empagliflozin / placebo is permanently discontinued during the Randomised Run-In period, the patient should permanently discontinue the trial. If one of the study medications (either empagliflozin/placebo or BI 690517/placebo) is permanently discontinued during the Treatment Period / after the second randomisation at Visit 5, the patient may continue to receive treatment with the other study medication and should continue with scheduled study visits according to the [Flowchart](#).

Treatment interruption

In the following case, all randomised study medication must be interrupted:

- severe SARS-COV-2 infection

In the following cases, the empagliflozin / placebo must be interrupted:

- complicated UTI
- symptomatic volume depletion

In the following cases, the BI 690517 / placebo must be interrupted:

- serum potassium $\geq 5.6 \text{ mmol/L}$ (see [section 4.2.1.1](#))
- serum potassium $\geq 5 \text{ mmol/L}$ if the patient is unable or unwilling to return to the investigational site (see [section 4.2.1.1](#))

In these cases, trial treatment could be restarted upon recovery if medically justified, please see [section 4.1.4](#).

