4.2.1.1 Management of serum potassium elevation

Increased potassium levels are not uncommon in patients with CKD and are often multifactorial in nature. A rise in serum potassium under treatment with BI 690517 cannot be excluded and therefore regular measurements of potassium levels are an integral part of the

visit schedule. For any episode of increased potassium level above 5.0 mmol/L, a clinical evaluation should be performed to make individual treatment decisions if a prompt intervention is required. For BI 690517 the dose might be adjusted to keep potassium levels in an acceptable range. The investigator should consider whether a down-titration is appropriate from a clinical perspective considering symptoms, relevant ECG changes, dynamics of potassium changes, intercurrent disorders, and lower ranges of eGFR. For detailed guidance on how to manage serum potassium elevations, please refer to [Table 4.2.1.1: 1](#).

Table 4.2.1.1: 1 Management of serum potassium

Serum Potassium	Actions (BI 690517 / placebo)
< 5.0 mmol/L	Continue on current dose if deemed appropriate (e.g. in absence of clinical symptoms or slow/small increase over time) For clinically relevant serum potassium increases to < 5.0 mmol/L, the investigator may consider interruption and/or down-titration of BI 690517 /placebo.
≥ 5.0 to <5.6 mmol/L	Option 1: Continue on current dose. Recheck K ⁺ within 72 hours. If levels continue to be ≥5.0 mmol/L, either continue dose with weekly monitoring, or follow Option 2 or Option 3. OR Option 2: Down-titration If down titration is deemed appropriate, the BI 690517 / placebo should be temporarily stopped and the next lower dose will be allocated by IRT as soon as possible. After restarting on a lower dose, investigator should recheck K ⁺ within 72 hours. If levels continue to be >5.0 mmol/L, permanently discontinue. OR Option 3: If down titration is considered inappropriate, permanently discontinue BI 690517 / placebo
≥ 5.6-< 6.0 mmol/L	Option 1: Interruption followed by down titration Study medication should be temporarily interrupted. Investigator should recheck K ⁺ every 72 hours and can restart study medication at the next lower dose once K ⁺ falls to < 5.0mmol/L. After restarting on a lower dose, investigator should recheck K ⁺ within 72 hours. If levels continue to be >5.0, permanently discontinue. OR Option 2: If down titration is considered inappropriate permanently discontinue BI 690517 / placebo

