≥ 6.0 mmol/L	Discontinue BI 690517 / placebo permanently.

In case of symptomatic hyperkalaemia initiation of potassium lowering treatment might be considered as medically indicated, like diuretics, potassium binding resins or other treatments as described in local or global guidelines for treatment of hyperkalaemia.

If BI 690517 or matching placebo must be permanently discontinued due to raised serum potassium, the patient may still continue to receive empagliflozin / matching placebo (see [section 3.3.4](#)).

In the event of elevated potassium ≥ 5 mmol/L, if the patient is unable or unwilling to return to the investigational site, for example during pandemic situation, the BI 690517 or matching placebo should be temporarily interrupted until the patient can return to the investigational site.

For patients taking potassium supplements, serum potassium should be monitored closely, and if serum potassium is ≥ 4.5 mmol/L, the investigator should consider reducing or discontinuing the potassium supplements, according to investigator judgement.

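### For a patient who cannot return to site, Protocol 6.2 interrupts BI 690517 only above 5 mmol/L potassium, while 3.3.4.1 and 4.2.1.1 interrupt at 5 mmol/L or above

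*Protocol*

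**What the plan says.** The rule for a patient with raised potassium who does not come back to the site appears in three places in the current protocol (Version 4.0).

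- **Section 3.3.4.1 (Discontinuation of trial treatment), under treatment interruption.** The list opens with "In the following cases, the BI 690517 / placebo must be interrupted". Its second entry is serum potassium of 5 mmol/L or above, "if the patient is unable or unwilling to return to the investigational site", with a pointer to 4.2.1.1.
- **Section 4.2.1.1 (Management of serum potassium elevation), after the table.** The threshold is again 5 mmol/L or above, "if the patient is unable or unwilling to return to the investigational site, for example during pandemic situation". The action is temporary interruption until the patient can return.
- **Section 6.2 (Details of trial procedures at selected visits), in the text on force majeure and remote conduct.** It reads "In the event of elevated potassium > 5 mmol/L, if the patient is unable or unwilling to return to the investigational site", and the action is that "the BI 690517 or matching placebo should be temporarily interrupted until the patient can return to the investigational site".

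Table 4.2.1.1:1, which governs potassium management in general, has an action band of "≥ 5.0 to <5.6 mmol/L". That band includes 5.0.

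**The concern.** A dosing rule written for patient safety should give the same answer wherever a site reads it. Here the condition and the action match, but the inequality sign in 6.2 differs from the other two sections.

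Section 6.2 is where a site would look when visits have to be run from home or remotely. Its potassium sentence has no cross-reference to 3.3.4.1 or 4.2.1.1. A site relying on it could leave a patient on BI 690517 at 5.0 mmol/L although 3.3.4.1 requires interruption.

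Potassium is also the leading mechanism-related risk for this drug. Section 1.4.2 promises close monitoring of it, and section 8.7 names potassium-related events as a particular focus of the data monitoring committee. Potassium may be at most 4.8 mmol/L at entry and again before the second randomisation, so 5.0 is only 5.0 − 4.8 = 0.2 mmol/L above the limit.

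**Working it through.** This is a comparison of decision rules. The plan gives no figure to reproduce, and no power, alpha or sample size calculation is involved.

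**Inputs, for a patient who is not able or willing to return**

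| Section | Trigger for interruption | Force | Action |
|---|---|---|---|
| 3.3.4.1 | K⁺ ≥ 5 mmol/L | must | interrupt BI 690517 / placebo; restart possible on recovery |
| 4.2.1.1 | K⁺ ≥ 5 mmol/L | should | interrupt temporarily until return to site |
| 6.2 | K⁺ > 5 mmol/L | should | interrupt temporarily until return to site |

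**Each rule applied at and around the boundary**

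| K⁺ (mmol/L) | 3.3.4.1 | 4.2.1.1 | 6.2 |
|---|---|---|---|
| 4.9 | 4.9 ≥ 5 false: not triggered | 4.9 ≥ 5 false: not triggered | 4.9 > 5 false: not triggered |
| 5.0 | 5.0 ≥ 5 true: interrupt | 5.0 ≥ 5 true: interrupt | 5.0 > 5 false: not triggered |
| 5.1 | 5.1 ≥ 5 true: interrupt | 5.1 ≥ 5 true: interrupt | 5.1 > 5 true: interrupt |

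The rules part company at 5.0 only.

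**Could the sections cover different situations?** No. Section 4.2.1.1 gives a pandemic as its example, and 6.2 deals with force majeure and other disruption. Sections 4.2.1.1 and 6.2 apply to the same kind of patient and prescribe the same temporary interruption.

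**Which section is out of line?** Two of the three statements of this rule use ≥ 5, including the mandatory one and the one in the dedicated potassium section. That is the main evidence. The table band starting at 5.0 is consistent with it but is weaker support, because 4.2.1.1 also uses a strict sign for two other rules: the prompt for clinical evaluation, and the recheck after down-titration.

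**Does it reach the analysis?** Protocol 7.2.2 lists four intercurrent events: discontinuation of BI 690517, down-titration of BI 690517, SGLT2 inhibitor use, and death. SAP 5.1 gives handling rules for the same four. Temporary interruption is not among them, so the sign does not change which UACR data enter the primary model.

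**The case against.** The best case on the other side accepts the mismatch and argues that it hardly matters.

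- **There is no true conflict of duties.** Section 6.2 is silent at 5.0; it does not instruct the site to continue. A site that interrupts at 5.0 complies with all three sections. This is correct. It limits the problem to a site that reads 6.2 in isolation.
- **The protocol tolerates dosing at 5.0 in ordinary patients.** In the table band starting at 5.0, the first option is to stay on the current dose with a recheck within 72 hours. Local-laboratory testing (6.2) and home blood collection (6.2.2) may make that recheck possible without a site visit. Section 6.2 also stops all randomised medication if remote visits or laboratory assessments cannot be done within the visit window, or if safety cannot be guaranteed. This lowers the practical risk. It does not override 3.3.4.1, which takes the option of continuing away from patients who do not come back.
- **Wording at 5.0 is mixed within 4.2.1.1.** This is true, and it is why the table should not carry the argument. The strict signs there belong to other rules, and the two direct restatements of this rule agree with each other.
- **The sign may have been lost when the PDF was read.** This cannot be fully excluded for a single character. The ≥ sign survives in 3.3.4.1 and 4.2.1.1, which makes a loss in 6.2 less likely, and the sponsor can settle it from the source file.
- **It is an editorial matter.** It is a wording inconsistency, and no design decision is in dispute. Because the wording decides whether a patient is dosed, it still merits correction.

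**Conclusion.** The concern holds as stated. Section 6.2 gives a different threshold from 3.3.4.1 and 4.2.1.1 for the same patient and the same action, and the difference bites at exactly 5.0 mmol/L.

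It is a minor safety-consistency error. The documents give neither the distribution of potassium on treatment nor the share of patients who could not return, so the number affected cannot be estimated. The protocol states its potassium thresholds to one decimal place. If laboratories report to one decimal as well, which is an assumption, 5.0 would be an ordinary result; with finer reporting, an exact tie would be rarer.

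No analysis, power or error-rate figure changes. The conclusion assumes that the sign in 6.2 is printed in the protocol as it appears in the text reviewed.

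**What to change.** In section 6.2, change the trigger from above 5 mmol/L to 5 mmol/L or above. This matches 3.3.4.1 and 4.2.1.1 and takes the more cautious reading. Adding a pointer from that sentence to 4.2.1.1 would help a site working from 6.2 to find the full potassium rules.

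The cost is one character in the protocol and a short clarification to sites. The SAP, sample size and data collection need no change.
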